8.3.3 Follow-up of AEs and SAEs

After the initial AE/AESI/SAE report, the Investigator is required to proactively follow each participant at subsequent visits/contacts. At the pre-specified study end-date, all SAEs, and AESIs (as defined in [Section 10.3](#)), will be followed until resolution, stabilization, the event is otherwise explained, or the participant is lost to follow-up (as defined in [Section 7.3](#)).

Stabilization is defined as an AE ongoing without any change for at least 3 months. Participants with an AE of Grade >1 will be further followed until the resolution of the AE to Grade 0-1 or starting of a new antineoplastic therapy, whichever occurs first.

Further information on follow-up procedures is provided in Appendix 3 ([Section 10.3](#)).

8.3.4 Regulatory reporting requirements for SAEs

- Prompt notification by the Investigator to the Sponsor of an SAE is essential so that legal obligations and ethical responsibilities towards the safety of participants and the safety of a study intervention under clinical investigation are met.

- The Sponsor has a legal responsibility to notify both the local regulatory authority and other regulatory agencies about the safety of a study intervention under clinical investigation. The Sponsor will comply with country-specific regulatory requirements relating to safety reporting to the regulatory authority, Institutional Review Boards (IRB)/Independent Ethics Committees (IEC), and Investigators.
- Serious adverse events that are considered expected will be specified in the reference safety information (IB for SAR444245).
- Investigator safety reports must be prepared for suspected unexpected serious adverse reactions (SUSARs) according to local regulatory requirements and Sponsor policy and forwarded to Investigators as necessary.
- An Investigator who receives an Investigator safety report describing an SAE, SUSAR or any other specific safety information (eg, summary or listing of SAEs) from the Sponsor will review and then file it along with the IB and will notify the IRB/IEC, if appropriate according to local requirements. It is the responsibility of the Sponsor to assess whether an event meets the criteria for a SUSAR, and therefore, should be expedited to regulatory authorities.

8.3.5 Pregnancy

- Details of all pregnancies in female participants and female partners of male participants will be collected after the start of study intervention and until 120 days (for Cohort A, B1, B2, B3, C, and D1) or 60 days (for Cohort D2) following cessation of study treatment, or 30 days following cessation of study treatment if the participant initiates another anticancer therapy.
- If a pregnancy is reported, the Investigator will record pregnancy information on the appropriate form and submit it to the Sponsor within 24 hours of learning of the female participant or female partner of male participant (after obtaining the necessary signed informed consent from the female partner) pregnancy.
- Abnormal pregnancy outcomes (eg, spontaneous abortion, fetal death, stillbirth, congenital anomalies, ectopic pregnancy) are considered SAEs and will be reported as such.
- The participant/pregnant female partner will be followed to determine the outcome of the pregnancy. The Investigator will collect follow-up information on the participant/pregnant female partner and the neonate, and the information will be forwarded to the Sponsor.
- Any post-study pregnancy-related SAE considered reasonably related to the study intervention by the Investigator will be reported to the Sponsor as described in [Section 8.3.4](#). While the Investigator is not obligated to actively seek this information in former study participants/pregnant female partner, he or she may learn of an SAE through spontaneous reporting.
- Any female participant who becomes pregnant while participating in the study will discontinue study intervention.

8.3.6 Cardiovascular and death events

Cardiovascular events that meet AESI criteria should be reported as such (see [Section 8.3.8](#) for details).

8.3.7 Disease-related events and/or disease-related outcomes not qualifying as AEs or SAEs

Not applicable.

8.3.8 Adverse event of special interest

Adverse event of special interest

An AESI is an AE (serious or nonserious) of scientific and medical concern specific to the Sponsor's product or program, for which ongoing monitoring and immediate notification by the Investigator to the Sponsor is required. Such events may require further investigation in order to characterize and understand them. Adverse events of special interest may be added, modified or removed during a study by protocol amendment.

The following events need to be reported as AESIs:

- Pregnancy of a female participant entered in a study as well as pregnancy occurring in a female partner of a male participant entered in a study with IMP/NIMP;
 - Pregnancy occurring in a female participant entered in the clinical trial or in a female partner of a male participant entered in the clinical trial. It will be qualified as an SAE only if it fulfills one of the seriousness criteria (see Appendix 3 [[Section 10.3](#)]).
 - In the event of pregnancy in a female participant, IMP should be discontinued.
 - Follow-up of the pregnancy in a female participant or in a female partner of a male participant is mandatory until the outcome has been determined (See Appendix 4 [[Section 10.4](#)])
- Symptomatic overdose (serious or nonserious) with IMP/NIMP
 - An overdose of IMP is defined as: increase of at least 30% of the dose to be administered in the specified duration or if the dose is administered in less than half the recommended duration of administration.
 - An overdose (accidental or intentional) with the NIMP is an event suspected by the Investigator or spontaneously notified by the participant (not based on systematic pills count) and defined as at least twice the intended dose within the intended therapeutic interval, adjusted according to the tested drug.
- An elevated AST or ALT lab value that is greater than or equal to $3 \times$ ULN and an elevated total bilirubin lab value that is greater than or equal to $2 \times$ ULN and, at the same time, an alkaline phosphatase lab value that is less than $2 \times$ ULN, as determined by way of protocol-specified laboratory testing or unscheduled laboratory testing*.

For Participants with HCC, please refer to substudy 03 Corhort C.

*Note: These criteria are based upon available regulatory guidance documents. The purpose of the criteria is to specify a threshold of abnormal hepatic tests that may require an additional evaluation for an underlying etiology. The trial site guidance for assessment and follow up of these criteria can be made available. It may also be appropriate to conduct additional evaluation for an underlying etiology in the setting of abnormalities of liver blood tests including AST, ALT, bilirubin, and alkaline phosphatase that do not meet the criteria noted above. In these cases, the decision to proceed with additional evaluation will be made through consultation between the study investigators and the Sponsor.

- Other project-specific AESIs
 - IRR Grade ≥ 2
 - CRS Grade ≥ 2
 - ICANS of any grade
 - VLS of any grade
 - SARS-CoV-2 infection/COVID-19 disease
 - Any immune-related AE Grade ≥ 3
 - Arrhythmia Grade ≥ 3

8.3.9 Guidelines for reporting product complaints

Any defect in the IMP/NIMP must be reported as soon as possible by the Investigator to the monitoring team that will complete a product complaint form within required timelines.

Appropriate information (eg, samples, labels or documents like pictures or photocopies) related to product identification and to the potential deficiencies may need to be gathered. The Investigator will assess whether or not the quality issue has to be reported together with an AE or SAE.

8.4 PHARMACOKINETICS

The sampling time-points for PK and ADA for/against SAR444245 and/or other IMPs may be updated during the course of the study based on the updated knowledge of drug behavior upon notification from the Sponsor.

[figure not shown]
Instructions for the collection and handling of biological samples will be provided by the Sponsor in the laboratory manual. The actual date and time (24-hour clock time) of each sample will be recorded while for samples to be collected at time of biomarker sampling, no specific time on the given day is necessary.

Instructions on the collection, processing, storage, and shipment of samples will be provided in the laboratory manual. Sample analysis will be performed at a laboratory designated by the Sponsor.

[figure not shown]
Samples collected for analyses of SAR444245 concentration may also be used to evaluate safety or efficacy aspects related to concerns arising during or after the study and any remaining plasma/serum volume may also be used for further exploratory analysis if deemed relevant.

[figure not shown]
For China, please see [Section 10.7](#) for details.

8.5 GENETICS AND/OR PHARMACOGENOMICS

8.6 BIOMARKERS

8.7 IMMUNOGENICITY ASSESSMENTS

The sampling time points for ADAs may be reduced or increased during the course of the study based on the updated knowledge of drug behavior and its immunogenicity, upon notification from the Sponsor.

Samples for the immunogenicity assessment of SAR444245 will be collected according to the PK flowcharts. Instructions for the collection and handling of biological samples will be provided by the Sponsor. Sample analysis will be performed at a laboratory designated by the Sponsor.

Samples will be screened and then confirmed for anti-drug antibodies and the titer of confirmed positive samples will be reported. Additional analyses may be performed to further characterize the immunogenicity of SAR444245.

[figure not shown]
Anti-drug antibody (ADA) samples remaining after determination of immunogenicity may be kept for possible exploratory analysis of biomarkers. The exploratory data will not be included in the study report but will be kept on file.

For China, please see [Section 10.7](#) for details.

8.8 HEALTH ECONOMICS

No health economics data will be collected.

8.9 USE OF BIOLOGICAL SAMPLES AND DATA FOR FUTURE RESEARCH

9 STATISTICAL CONSIDERATIONS

Please refer to substudies protocols for additional statistical considerations.

9.1 STATISTICAL HYPOTHESES

This study is designed to assess antitumor activity, safety, pharmacokinetic (PK), pharmacodynamic (PDy) and immunogenicity data on SAR444245 when combined with other anticancer therapies in participants with gastro-intestinal cancer. As the study is not intended to explicitly test a hypothesis, calculations of power and Type I error were not considered in the study design.

9.2 SAMPLE SIZE DETERMINATION

Number of participants to be enrolled in each cohort is described in the individual substudy.

9.3 POPULATIONS FOR ANALYSES

The following populations for analyses are defined ([Table 3](#)):

Table 3 - Populations for analyses

Population	Description
Exposed	Exposed population will include all participants who have given their informed consent and received at least one dose (even incomplete) of IMP (SAR444245 or other anticancer therapies).
Efficacy	Efficacy population will include all participants from the exposed population with at least one evaluable post-baseline tumor assessment or who permanently discontinued study treatment.
PK	The PK population will include all participants from the exposed population with at least 1 PK concentration available after the first dose of study intervention.
PDy	The PDy population will include all participants from the exposed population with at least 1 PDy parameter assessed after the first dose of study intervention.

9.4 STATISTICAL ANALYSES

The statistical analysis plan (SAP) will include a more technical and detailed description of the statistical analyses described in this section. This section is a summary of the planned statistical analyses of the most important endpoints including primary, key secondary endpoints, and exploratory endpoints.

9.4.1 General considerations

This study is not intended to explicitly test a hypothesis, 90% CIs will be provided for primary and secondary efficacy endpoints for descriptive purposes only.

All efficacy analyses will be performed on the efficacy population and analyzed by cohort and pooled cohorts (if applicable). Objective response rate, as well as all other efficacy variables will be derived using the local radiologist's/Investigator's assessment for all cohorts. Unless otherwise specified, the assessments are based on RECIST 1.1.

All safety analyses will be performed on the exposed population by cohort and overall (if applicable). A baseline value will be defined as the latest value or measurement taken up to the first administration of the IMP.

The analysis period will be divided into 3 segments:

- The pre-treatment period is defined as the time from when the participants give informed consent to the first administration of the IMP.
- The on-treatment period (ie, treatment-emergent period) is defined as the time from the first administration of IMP up to 30 days after the last administration of IMP.
- The post-treatment period is defined as the time from the 31 days after the last administration of IMP.

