Screening Period: up to 28 days

Treatment Period: enrolled participants will receive continuous treatment until PD, unacceptable adverse event (AE) or other full permanent discontinuation criteria as described in [Section 7](#); or completion of Cycle 35 (if applicable).

End of Treatment and Follow-up: End of Treatment Visit will occur 30 days \pm 7 days from last IMP administration or prior to initiation of further therapy, whichever comes first.

Participants will then enter the **Observation Period** and will be followed differently depending on the reason leading to **End of Treatment (EOT)**.

1. Participants who discontinue study treatment **without PD** or who complete 35 cycles of treatment without PD will be followed every 3 months \pm 7 days from last IMP administration, for safety (as per Schedule of Activities [SoA]) and tumor imaging assessments until PD, start of another anticancer therapy, final cohort cut-off, whichever comes first, before moving to the Survival Phone Call Follow-Up Period.
2. Participants who discontinue study treatment **with PD** will be followed for safety in the Follow-Up Visit 1 occurring 3 months \pm 7 days from last IMP administration, before moving to the Survival Phone Call Follow-Up Period.

Participants who move into the **Survival Phone Call Follow-Up Period** will be contacted by telephone every 3 months \pm 14 days to assess for survival status. Updated survival status may be requested by the Sponsor at any time during the study. Survival Phone Call Follow-up will continue until death, participant request to discontinue from follow-up, or cut-off date for the given cohort final analysis has been reached, or upon cancellation of Survival follow-up in the given cohort at the discretion of the Sponsor at any prior timepoint, whichever occurs first.

The cohort cut-off for the primary ORR endpoint analysis in each individual cohort is estimated to be approximately 9 months from the date of the last participant first infusion. This would allow the possibility to observe the response of the last participant for 6 months, assuming there is a response at first treatment assessment.

After the cohort cut-off date for the primary ORR analysis, participants can continue to receive IMP, if clinical benefit is observed, until full permanent discontinuation criteria described in **Section 7** are met and will continue to undergo all assessments as per the study schedule of activities.

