1.3 SCHEDULE OF ACTIVITIES (SOA)

Evaluation ^a	Screening	Treatment Period ^b				End of Treatment	Observation Period ^c			Survival Phone Call Follow-up ^d	Notes
		Cycle 1		Cycle 2 and beyond ^e			EOT Visit	Follow-Up	Follow-Up	Follow-Up	
		Visit 1	Visit 2	Visit 3+				Phone Call FU			
Cycle Day (Visit window in Days)	D-28 to D-1	D1	D8 ^f (±1)	D15 ^f (±1)	D1 (±3)	30 days (+/- 7 days) after last IMP or at initiation of further therapy	3 months after last IMP admin ±7 days	6 months after last IMP admin ±7 days	Every 3 months after FU visit 2 ± 7 days	Every 3 months +/- 14 days	
Informed consent	X										
Inclusion and exclusion criteria	X										
IRT contact	X	X			X	X					
Demography, medical/surgical and disease history	X										See Section 8
Body Weight / Height ^g	X	X	X	X	X	X	X				
Full physical examination	X					X					See Section 8.2.1
Directed Physical examination		X	X	X	X		X				See Section 8.2.1
Vital Signs	X	X	X	X	X	X	X				See Section 8.2.2
Performance status (ECOG)	X	X	X	X	X	X	X				
SpO ₂	X	As clinically indicated									

Evaluation ^a	Screening	Treatment Period ^b				End of Treatment	Observation Period ^c			Survival Phone Call Follow-up ^d	Notes
		Cycle 1			Cycle 2 and beyond ^e		Follow-Up	Follow-Up	Follow-Up		
		Visit 1	Visit 2	Visit 3+			Phone Call FU				
Cycle Day (Visit window in Days)	D-28 to D-1	D1	D8 ^f (±1)	D15 ^f (±1)	D1 (±3)	30 days (+/- 7 days) after last IMP or at initiation of further therapy	3 months after last IMP admin ±7 days	6 months after last IMP admin ±7 days	Every 3 months after FU visit 2 ± 7 days	Every 3 months +/- 14 days	
Laboratory and other investigations											
12-Lead ECG	X	X	As clinically indicated								See Section 8.2.3
LVEF	X	As clinically indicated									See Section 8.2.3
Troponin	X	As clinically indicated		X (Cycle 4 Day 1)	As clinically indicated						See Section 8.2.3 and Section 10.2
Pregnancy test	X	X			X	X	X	X			See Section 8.2.5 and Section 10.2
Hepatitis serology, CD4 counts and viral load	X ^h	As clinically indicated									See Section 10.2 and Section 10.7
Hematology	X	X	X	X	X	X	X				See Section 10.2
Coagulation	X	As clinically indicated									See Section 10.2
Blood Chemistry	X	X	X	X	X	X	X				See Section 10.2

[figure not shown]
Evaluation ^a	Screening	Treatment Period ^b				End of Treatment	Observation Period ^c			Survival Phone Call Follow-up ^d	Notes	
		Cycle 1			Cycle 2 and beyond ^e	EOT Visit	Follow-Up	Follow-Up	Follow-Up	Phone Call FU		
							Visit 1	Visit 2	Visit 3+			

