8.3.1 Time period and frequency for collecting AE and SAE information

All AEs, including adverse events of new onset, as well as worsening of baseline signs and symptoms will be collected throughout study period, from the signing of the informed consent form (ICF) until **30 days** following cessation of study treatment.

All SAEs and AESIs will be collected throughout the study period, from the signing of the informed consent form (ICF) until **90 days** following last administration of study treatment.

All SAEs and AESI will be recorded and reported to the Sponsor or designee immediately and under no circumstance should this exceed 24 hours, as indicated in Appendix 3 ([Section 10.3](#)). The Investigator will submit any updated SAE data to the Sponsor within 24 hours of it being available.

Investigators are not obligated to actively seek information on AEs or SAEs after conclusion of the study participation. However, if the Investigator learns of any SAE, including a death, at any time after a participant has been discharged from the study, and he/she considers the event to be reasonably related to the study intervention or study participation, the Investigator must promptly notify the Sponsor.

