9.4.3.5 Adverse events

All AEs will be categorized according to NCI-CTCAE v5.0 (except for CRS and ICANS that will be graded using ASTCT criteria) and classified by system organ class (SOC) and Preferred Term (PT) according to the latest available version of the Medical Dictionary for Regulatory Activities (MedDRA).

- Pre-treatment AEs are defined as any AEs occurring during the pre-treatment period.
- Treatment-emergent AEs are defined as AEs that develop, worsen (according to the Investigator's opinion), or become serious during the treatment-emergent period.
- Post-treatment AEs are defined as AEs that are reported during the post-treatment period.

For participants with multiple occurrences of the same PT, the maximum grade will be used.

The primary focus of AE reporting will be on TEAEs. Pre-treatment and post-treatment AEs will be described separately.

Treatment-emergent adverse events:

An overall summary of TEAEs will be provided. The number and percentage of participants experiencing any of the following will be provided:

- TEAEs
- Grade ≥ 3 TEAEs
- Grade 5 TEAEs (any TEAE with a fatal outcome during the treatment-emergent period)
- Serious TEAEs
- Serious treatment-related TEAEs
- TEAEs leading to permanent partial intervention discontinuation (any of the IMP components)
- TEAEs leading to permanent full intervention discontinuation
- Treatment-related TEAEs
- Treatment-related TEAEs Grade ≥ 3

Number and percentage of participants experiencing TEAEs by primary SOC and PT will be summarized by NCI-CTCAE v 5.0 or ASTCT grade (all grades and Grade ≥ 3). Missing grades, if any, will be included in the "all grades" category. Similar summaries will be prepared for treatment-related TEAEs, TEAEs leading to permanent discontinuation of SAR444245, or permanent discontinuation of other anticancer therapies in combination, TEAEs leading to full intervention discontinuation, TEAEs leading to dose modification, serious TEAEs, TEAEs with fatal outcome, AESIs, and AEs/SAEs occurring during the post-treatment period. In addition, the number (%) of participants with any Grade 5 AE (TEAE and post-treatment) will be summarized.

The following deaths summaries will be generated:

- Number and percentage of participants who died by study period (treatment-emergent period, post-treatment period) and reasons for death (disease progression, AE, or other reason).
- All TEAEs leading to death by primary SOC and PT showing number and percentage (%) of participants.

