9.4.3.6 Clinical Laboratory evaluations

Clinical laboratory values will be analyzed after conversion into standard international units. International units will be used in all listings and tables.

Hematology and clinical chemistry results will be graded according to the NCI-CTCAE v 5.0, when applicable. Number and percentage of participants with laboratory abnormalities (all grades and by grade) using the worst grade during the treatment period will be provided for the exposed population.

When the NCI-CTCAE v 5.0 grading scale is not applicable, the number of participants with laboratory abnormality out-of-normal laboratory range value will be displayed.

For laboratory variables graded by NCI-CTCAE:

- The number (%) of participants with abnormal laboratory tests at baseline will be presented by grade.
- The number (%) of participants with abnormal laboratory tests during the treatment emergent period will be summarized by grade. When appropriate, the number (%) of participants with abnormality of any grade and with Grade 3-4 abnormalities will be provided.

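### Laboratory values from a compliant End of Treatment visit on days 31-37 fall outside the on-treatment worst-grade summary, and no other laboratory summary is stated for them

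*Protocol*

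**What the plan says.** Section 9.4.1 of the master protocol divides follow-up into three segments. The on-treatment, or treatment-emergent, period "is defined as the time from the first administration of IMP up to 30 days after the last administration of IMP". The next segment follows directly: "The post-treatment period is defined as the time from the 31 days after the last administration of IMP".

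The Schedule of Activities (section 1.3) times the EOT visit at "30 days (+/- 7 days) after last IMP or at initiation of further therapy". The synopsis and section 4.1 give the same window, counted "from last IMP administration or prior to initiation of further therapy, whichever comes first". Hematology, blood chemistry, urinalysis and vital signs are marked at that visit.

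Laboratory abnormalities are part of the secondary safety endpoint. Section 9.4.3.6 says that graded hematology and chemistry results "using the worst grade during the treatment period will be provided for the exposed population". The synopsis ties the same summary to the on-treatment period, and a later bullet in 9.4.3.6 refers to the treatment-emergent period, so the 9.4.1 definition governs.

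For adverse events, section 9.4.3.5 says: "Treatment-emergent AEs are defined as AEs that develop, worsen (according to the Investigator's opinion), or become serious during the treatment-emergent period". Section 8.3.1 collects all AEs to 30 days after treatment stops, and SAEs and AESIs to 90 days after the last administration.

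**The concern.** The analysis period ends on a fixed day that is also the centre of the EOT visit window. A draw on day 29 and a draw on day 33 both comply with the schedule, yet only the first enters the worst-grade summary. Suppose the last dose is on day 0 and a new Grade 3 ALT is found at an EOT visit on day 33. The visit is on time, but the value counts as post-treatment and is not in the on-treatment table. Section 9.4.3.5 promises a post-treatment summary for AEs. Section 9.4.3.6 promises none for laboratory values.

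The draw matters because of where it sits. After Cycle 1, hematology and chemistry are scheduled only on Day 1 of each cycle up to Cycle 12, then every other cycle (section 10.2, Table 4, note a). For a participant whose last dose is in Cycle 2 or later, the EOT draw is normally the first scheduled set after that dose. The next is Follow-Up Visit 1, at 3 months. Whether an abnormality after the last dose is counted can therefore turn on when the appointment was booked.

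**Working it through.** The documents give no figure for the share of EOT data inside or outside the on-treatment period, so there is nothing of the plan's own to reproduce.

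**Inputs from the protocol**
- End of the on-treatment period: day 30 after last IMP (9.4.1).
- EOT window: day 30 ± 7, that is days 23 to 37 (1.1, 1.3, 4.1), brought forward if further therapy starts first.
- Hematology and chemistry: Cycle 1 Days 1, 8 and 15, then Day 1 of each cycle to Cycle 12 (10.2).
- Participants per cohort: about 40 (substudy 01, section 9.2).

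**Inputs that must be assumed**
- How visit days are spread within the window.
- How many EOT visits are brought forward to day 30 or earlier by further therapy.

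**Step 1, count of days.** The window has 37 − 23 + 1 = 15 days. Days 31 to 37 are 7 of them, and 7/15 = 46.7%. This counts permitted days, not data.

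**Step 2, share of EOT visits after day 30.** Each assumption is varied on its own.

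| Assumption | Share on days 31-37 |
|---|---|
| Uniform over days 23-37 | 47% |
| Normal around day 30, SD 4 days | 45% |
| Normal around day 30, SD 3 days | 43% |
| Normal around day 30, SD 2 days | 40% |
| Normal around day 30, SD 1 day | 31% |
| Uniform, 20% brought forward: 0.80 × 7/15 | 37% |
| Uniform, 30% brought forward: 0.70 × 7/15 | 33% |
| Uniform, 50% brought forward: 0.50 × 7/15 | 23% |

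The range is 23% to 47%. If all 40 participants in a cohort have an EOT draw, that is 40 × 0.233 = 9 to 40 × 0.467 = 19 laboratory sets. The two effects together would give less: with SD 1 day and 50% brought forward, 0.31 × 0.50 is about 15%.

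**Step 3, weight among all post-dose draws.** A participant treated for 3 cycles has 5 scheduled draws after the first dose: Cycle 1 Days 8 and 15, Day 1 of Cycles 2 and 3, and EOT. Under the uniform assumption the expected loss is (7/15)/5 = 9% of these. After 6 cycles there are 8 draws and the loss is (7/15)/8 = 6%. A worst grade is a maximum over all draws, so many excluded samples would change nothing. The loss is concentrated on the one scheduled draw that normally follows the final dose.

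**Step 4, adverse events.** An AE is placed by when it develops, worsens or becomes serious. An event that starts on day 28 and is recorded at a visit on day 35 is still treatment-emergent. The visit date removes nothing.

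**Step 5, after the change.** If in-window EOT laboratory values count as on-treatment, 15 of 15 permitted days are covered instead of 8 of 15, and no compliant EOT draw is excluded.

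**The case against.** The strongest case against has four parts.

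*A 30-day period is clear and consistent, and the detail belongs in the SAP.* A 30-day treatment-emergent period is indeed not wrong in itself, and section 9.4 calls itself a summary. But the protocol fixes both boundaries, day 30 and day 31. An SAP that counted day 33 as on-treatment would contradict 9.4.1. This is a stated rule, not a detail left open.

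*The abnormal value does not disappear.* This is largely right. Clinically relevant changes are recorded as AEs, and clinically significant values are repeated (8.2.4). Immune-related AEs of Grade 3 or higher are AESIs (8.3.8), collected to day 90. Section 7.1.1.1 adds rechecks before a decision to discontinue and, where possible, an assessment afterwards. Some participants will also have a Day 1 draw for a cycle that is then not given. None of this puts the EOT value into the laboratory table.

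*The scope is narrow.* This stands. The worst-grade summary covers graded hematology and chemistry. The vital-sign analysis in 9.4.5 states no period, so exclusion of vital signs is not documented.

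*AEs are not lost.* This also stands. A reader might infer that safety data in general drop out, or that the AE collection limit clashes with the EOT window. The documents do not support that. AEs go by onset; the section 8.3.1 rule beginning "All AEs, including adverse events of new onset, as well as worsening of baseline signs and symptoms will be collected throughout study period" ends at 30 days and so matches the analysis period; and the rule beginning "All SAEs and AESIs will be collected throughout the study period" runs to 90 days. AEs and SAEs in the post-treatment period have their own summary. An AE that starts on days 31-37 is outside the risk window by design.

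**Conclusion.** The point holds for graded hematology and chemistry. As written, results from a compliant EOT visit on days 31-37 are excluded from the on-treatment worst-grade summary, and no post-treatment laboratory summary is stated.

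Its size is uncertain. A reader might conclude from 7 of 15 days that close to half of the EOT data are lost. That would need visits spread evenly over the window and none brought forward by further therapy, and the documents give no distribution of visit days. Varying one assumption at a time gives roughly one quarter to just under one half of EOT sets, and less if visits both cluster tightly and are often brought forward. The effect on the table itself is smaller still, because the EOT draw is one of several and not every excluded sample would raise a worst grade.

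This is a modest defect in a secondary safety summary. It does not touch the primary endpoint or the TEAE tables. It is worth correcting because it makes the count depend on appointment timing, and the correction is cheap.

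**What to change.** Keep the 30-day treatment-emergent period and the 30-day collection limit for AEs as they are. Add one sentence to 9.4.1 and 9.4.3.6, carried into the SAP: for the laboratory summaries only, values from an EOT visit done within its window (up to day 37 after the last IMP, and before any further anticancer therapy) count as on-treatment. At the same time, use one term for the laboratory period in the synopsis and 9.4.3.6, which now vary between treatment, on-treatment and treatment-emergent.

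Do not redefine the whole on-treatment period to run to the EOT visit. Each participant's TEAE window would then last 30 to 37 days depending on when the visit was booked, and AE classification, which does not now depend on visit date, would start to do so.

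The cost is one sentence in each place. The laboratory window becomes up to 7 days longer for some participants, so abnormality rates may rise slightly.
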